## 7.2.1.2 Methods of Assessment

Spirometry will be performed using standard techniques specified by the American Thoracic Society and the European Respiratory Society (Miller et al 2005).

# 7.2.2 Respiratory Examination

# 7.2.2.1 Overview of Variables

Respiratory rate, pulse oximetry data, and related symptoms, such as cough, will be recorded before performing each spirometry (at baseline and after collecting the breath specimen at 10 and 30 minutes). Auscultation, noting the presence of wheezing and crackles, will be performed at baseline and at any assessment at which FEV1 decreases at least 20% from baseline.

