**Table 1 Dose Escalation Rules** 

Condition within 24 hours after administration of study drug	Number of DLTs/ Subjects in Cohort	Action
If no subject experiences DLT	0/3	Enroll three subjects at the 50 mg dose level
If one subject experiences DLT	1/3	Enroll three additional subjects at the 20 mg dose
If no additional subject experiences DLT	1/6	Enroll three subjects at the 50 mg dose level
If more than one subject experiences DLT	>1/6	Stop enrollment

Subjects will be receive C-urea 20 mg and 50 mg unless enrollment stops because of DLT. DLT Dose-limiting toxicity.

Sputum will be collected from each subject with CF before administering study drug in order to identify bacterial flora using two standard microbiologic methods. The first is a quantitative method in which colonies are stained and counted, the second is a colorimetric method in which a sample is plated in a medium that changes to a blue color as its pH is increased by the production of ammonia, a by-product of the urease-catalyzed degradation of urea.

The pharmacokinetics of the production of C-carbon dioxide will be characterized by determining the isotopic ratio of C to C in exhaled carbon dioxide of subjects in each part before study drug administration and at 5, 10, and 15 minutes.

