# 3.1.3.1 Dose-limiting Toxicity

The following significant respiratory events will be considered DLTs (Rosenfeld et al 2011):

- an absolute decrease from baseline FEV1 of 20% of baseline or greater
- an absolute decrease from baseline oxygen saturation of at least 10%
- an increase from baseline respiratory rate of 10 breaths per minute for more than 2 minutes during quiet breathing
- new wheezes or rales on examination.

In addition to these events that are mandated DLT, the data safety monitor may determine any serious adverse event attributed to study drug to be dose limiting.

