combined with immediate release of C-carbon dioxide enables the production of a signal. Because a 75 mg oral dose of C-urea is sufficient to reliably produce a measurable amount of exhaled C-carbon dioxide in patients infected with stomach *H. pylori*, which requires the carbon dioxide produced by the catalyzed hydrolysis of urea in the stomach to be absorbed into the blood stream and transported to the lung, it is likely that a 50 mg dose administered to the lung directly will produce a reliably measurable signal. The suitability of a lower dose, 20 mg dose, C-urea will also be tested.

In addition to mandatory rules that stop dose escalation in the event of DLT, dose escalation may also be stopped at the discretion of the data safety monitor.

Albuterol is standard therapy for relief of bronchospasm (Eng et al 1996) and also for the prevention of bronchospasm in diseases such as exercise-induced asthma (Raissy et al 2008). Patients with CF are frequently pretreated with albuterol if a therapy may produce bronchospasm, e.g., inhalation of 7% saline. Although nebulized isotonic solutions are not expected to produce bronchospasm, subjects with CF will be pretreated with albuterol because of the potential of mild bronchospasm induced from irritation of lung pathogens at the time of study drug administration.

The characterization of the pharmacokinetics of C-carbon dioxide will inform the useful time interval during which the isotopic ratio of C to C can be measured after administration of study drug in patients with lung infections (Otsuka America Pharmaceutical, Rockville, Maryland). Multiple breath specimens will be obtained at 15 minutes to estimate intra-patient variability.

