## 3.2.2 **Duration of Study**

Subjects will participate in the study for approximately 9 days, up to 7 days between the screening visit and the study visit plus a follow-up visit 24 hours after study drug administration. Subjects will receive a single dose of study drug and remain in the clinic for at 30 minutes for evaluation and observation. Subjects will be discharged from the study site after 30 minutes or thereafter when oxygen saturation levels and FEV1 values return to baseline and coughing symptoms are resolved. Twenty-four hours after administration of study drug, subjects will be contacted by telephone for a safety evaluation by study personnel. If an adverse event is

reported at the telephone contact, the subject will be asked to return to the clinic for an evaluation.

A 24-hour period will separate dose escalations. Thus, the study is anticipated to be completed within approximately 4 to 8 weeks after the first subject enrolls.

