# 6. VISIT SCHEDULE

The schedule of assessments and procedures are summarized in Table 4.

Table 4 Schedule of Procedures and Assessments for Dose-ranging Study

Assessment/Procedure	Screening (Day -7 to Day -1)	Day 1	Follow-up a
Informed consent	X		
Inclusion/exclusion criteria	X	X	
Medical history	X		
Concomitant medications, including all medications taken within the last 48 hours	X	X	X
Twelve-lead electrocardiogram	X		
Helicobacter pylori serology	X		
Urine pregnancy test (child-bearing females)		X	
Five-minute vital signs measurements c		X	
Respiratory examination (respiration rate, auscultation, pulse oximetry, and related symptoms, such as cough)		X	
Perform spirometry	Xb	X	
Administer albuterol (subjects with cystic fibrosis only)		X	
Perform spirometry d		X	
Obtain sputum specimen		Xe	
Perform breath test f		X	
Assess adverse events		X	Xg

<sup>a Subjects will be contacted by telephone 24 hours after administration of study drug for a follow-up assessment.

b Spirometry does not need to be performed at the screening visit if performed within the past 14 days.

<sup>c Heart rate, systolic and diastolic blood pressure, and body temperature will be recorded before study drug administration to assist in the determination that enrolled subjects are in generally good health.

d Spirometry will be performed before and at 10 and 30 min after the end of study drug administration. In addition, only for subjects with cystic fibrosis, spirometry will be performed before and  $10 \pm 2$  minutes after pre-treatment with albuterol.

<sup>e Sputum specimens will be collected immediately after performing baseline spirometry only from subjects with cystic fibrosis. Sputum specimens will be cultured to determine the identity and number of pathogens, and will also be qualitatively analyzed nonselectively for the presence of urease-producing bacteria using a colorimetric assay.

f Study drug will be administered immediately following spirometry, or for subjects with cystic fibrosis, the collection of sputum. Five baseline exhaled breath specimens will be obtained immediately before administration of  $^{13}$ C-urea. Exhaled breath specimens will be collected at  $5 \pm 1$ ,  $10 \pm 2$ ,  $15 \pm 2$  (in triplicate at this timepoint only) after administration of  $^{13}$ C-urea and sent within 24 h after collection to the central laboratory for analysis.

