# 6.2 ACTIVE TREATMENT (DAY 1)

- 1. Review inclusion and exclusion criteria.
- 2. Document all medications taken within the last 48 hours.
- 3. Perform a urine pregnancy test on women of child-bearing potential.
- 4. Record 5-minute sitting vital signs measurements (heart rate, systolic and diastolic blood pressure, and body temperature).
- 5. Perform respiratory examination (respiration rate, auscultation [presence of wheezing and crackles], pulse oximetry, and related symptoms, such as cough) (Section 7.2.1).
- 6. Perform spirometry (Section 7.2.1).
- 7. Administer albuterol, only to subjects with CF (Section 5.1.4).
- 8. Perform baseline spirometry  $10 \pm 2$  minutes after administering albuterol to subjects with CF only (Section 7.2.1).
- 9. For subjects with CF only, collect sputum specimen.
- 10. Collect five breath specimens. Record the clock time at which the sample was collected on two self-adhesive stickers. Place one sticker on the collection bag and the other on the CRF (Section 7.1.2.1).
- 11. Administer study drug by inhalation (Section 5.1.3). Record the clock time at the beginning and end of study drug administration.
- 12. Measuring time from the end of the inhalation of study drug, collect breath specimens at  $5 \pm 1$ ,  $10 \pm 2$ ,  $15 \pm 2$  minutes (three specimens at this time point only) after the inhalation of study drug is completed. Record the clock time of each breath collection on two self-adhesive stickers. Place one sticker on the collection bag and the other on the CRF (Section 7.1.2.1).
- 13. Perform spirometry after collecting the breath specimen at 10 and 30 minutes after the end of study drug administration (Section 7.2.1).
- 14. Assess adverse events (Section 8).

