# 7.2.2.2 Methods of Assessment

Respiratory rate will be determined by counting the number of breaths in one minute. Arterial blood saturation will be determined by oximetry; the same location will be used for each individual subject. The number of coughs in the 90-second interval following the end of the administration of study drug will be recorded in the CRF (Koskela et al 2005). Wheezing and crackles will be noted when auscultation is performed.

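### No oximetry reading is required during inhalation or for at least about 8 minutes after it, although a 10% saturation fall is a mandated dose-limiting toxicity; two spot readings would narrow the gap cheaply

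*Protocol*

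**What the plan says.** Section 7.2.2.1 sets the oximetry schedule by reference to spirometry: "Respiratory rate, pulse oximetry data, and related symptoms, such as cough, will be recorded before performing each spirometry". The spirometry times are in Table 4, footnote d ("Spirometry will be performed before and at 10 and 30 min after the end of study drug administration") and in section 6.2, step 13 ("Perform spirometry after collecting the breath specimen at 10 and 30 minutes after the end of study drug administration"). Time zero is the end of inhalation, and breath specimens are due at 5 ± 1, 10 ± 2 and 15 ± 2 minutes (section 6.2, step 12).

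Section 3.1.3.1 lists four respiratory events as mandated DLTs. One is "an absolute decrease from baseline oxygen saturation of at least 10" percent. It carries no minimum duration, whereas the respiratory-rate criterion in the same list does.

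For a 20 mg cohort with one DLT in three, Table 1 says "Enroll three additional subjects at the 20 mg dose"; with none in three, the study moves to 50 mg. Oximetry is also part of the primary safety endpoint (section 3.1.1).

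On expected reactions, section 3.2 states that nebulized isotonic solutions are not expected to produce bronchospasm. It nevertheless gives CF subjects albuterol because of the "potential of mild bronchospasm induced from irritation of lung pathogens at the time of study drug administration".

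**The concern.** The protocol makes a saturation fall an event that can change the course of escalation, but requires no saturation measurement in the period closest to exposure. Where the protocol does foresee a reaction, in CF subjects, it places it around dosing. A fall of at least 10% that occurred during or shortly after nebulization and recovered before the 10-minute assessment would meet the DLT definition, yet no required reading would show it.

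At stake is the DLT count in cohorts of three, where one event changes the Table 1 action. This is also the first human study of this breath test (section 1.5), so the early post-dose safety record has value beyond the escalation decision.

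**Working it through.** **Inputs (minutes from the end of inhalation)**

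- Breath specimens: 5 ± 1, 10 ± 2, 15 ± 2 (section 6.2, step 12; Table 4, footnote f; section 7.1.2.1).
- Post-dose spirometry: after the specimen at 10, and at 30 (section 6.2, step 13; Table 4, footnote d). No window of its own is given.
- Oximetry: before each spirometry (section 7.2.2.1).
- Cough count: the first 90 seconds, that is 1.5 minutes (section 7.2.2.2).
- Length of inhalation: not stated; it runs until the solution is used up (section 5.1.3).

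**Step 1: the schedule as written.** The first post-dose reading follows the 10 ± 2 minute specimen. Earliest time: 10 − 2 = 8. Nominal time: 10. There is no latest time. The specimen window closes at 10 + 2 = 12, but oximetry comes after the specimen and has no window, so 12 is not a ceiling. The stretch without a required reading is the whole of inhalation (length unknown) plus at least 8 minutes. The interval back to the last pre-dose reading is longer still, because baseline spirometry, five breath specimens and, in CF subjects, sputum collection come in between.

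**Step 2: do other required checks cover the window?** FEV1 is first measured after dosing at the same 10-minute point, and so is respiratory rate. Post-dose auscultation is required only where FEV1 has fallen by at least 20% (section 7.2.2.1). None of the four mandated DLT criteria therefore has a scheduled check before about 8 minutes. The only earlier timed safety measure is the cough count, and cough is not a listed DLT.

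**Step 3: the schedule with two added readings.**

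- First reading, with the cough count: 0 to 1.5.
- Second reading, at the 5 ± 1 specimen: 5 − 1 = 4 to 5 + 1 = 6.
- Gap between these two: 4 − 1.5 = 2.5 to 6 − 0 = 6.
- Gap from the second to the 10-minute reading: nominally 10 − 5 = 5, at least 8 − 6 = 2, with no upper limit for the reason in step 1.
- Required readings after the start of inhalation: 2 + 2 = 4, up from 2.
- Gap from the 10- to the 30-minute reading: nominally 30 − 10 = 20, unchanged.

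**Step 4: what one missed event would do.** If a single saturation DLT in a 20 mg cohort of three went unrecorded, the count would be 0/3 instead of 1/3. The Table 1 action would be escalation to 50 mg instead of three more subjects at 20 mg.

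**Step 5: the cost in false alarms (assumed rates, not from the documents).** Two added readings in each of three subjects make 3 × 2 = 6 per cohort. If each gave a spurious fall past the threshold with probability *a*, independently, the chance of at least one is 1 − (1 − *a*)^6.

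| Assumed *a* | Chance of at least one spurious fall per cohort |
|---|---|
| 0.5% | 1 − 0.995^6 = 3.0% |
| 1% | 1 − 0.99^6 = 5.9% |
| 2% | 1 − 0.98^6 = 11.4% |

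These are figures before any repeat reading. If every spurious value were recognized and repeated, and the repeat were independent, the rate per reading would be *a* squared. For *a* = 1% that gives 1 − (1 − 0.0001)^6, about 0.06% per cohort. Real artefacts are not fully independent, so this is the favorable end.

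**The case against.** The strongest objection is that this is a preference about sampling times. Sections 6.2, 7.2.2.1 and Table 4 agree with one another, and 10 and 30 minutes are times a small study may choose. The sentence in section 3.2 that mentions bronchospasm begins by saying isotonic solutions are not expected to cause it, and nothing links mild bronchospasm to a 10% saturation fall. The first cohorts have no pulmonary history (section 4.1.1) and CF subjects receive albuterol beforehand (section 5.1.4). Dosing is supervised (section 5.3), subjects "remain in the clinic for at 30 minutes for evaluation and observation" (section 3.2.2), and the data safety monitor sees clinical data daily (section 8.5). Table 1 counts DLTs over 24 hours, and section 3.1.3.1 does not confine them to scheduled readings, so a value taken by attending staff counts. FEV1, the more direct measure of bronchospasm, would still first be measured at 10 minutes.

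Most of this stands and sets the weight of the point. It makes a missed event less likely, but none of these provisions requires an early saturation value, and the monitor can review only values that were taken.

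A reader might infer three stronger things, which the documents do not support:

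- That the protocol contradicts itself. It does not; the schedule is coherent and simply starts late.
- That early saturation falls would go unobserved. Unscheduled readings are neither forbidden nor excluded from the DLT count, and a fall lasting to the 10-minute assessment would be recorded.
- That a probability of wrongful escalation can be stated. The protocol gives no rate of saturation DLTs and no share of them confined to the early window, so any such figure would only return its own assumptions.

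The objection to adding a reading in the middle of nebulization also stands. It would risk interrupting delivery and adding motion artefact, so it is not proposed.

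**Conclusion.** The point holds as a cheap improvement to the safety schedule, for consideration. No saturation value is required during inhalation or for at least about 8 minutes (nominally 10) after it, while a fall of at least 10% of any duration is a mandated DLT. An early fall that recovers is captured only by an unscheduled reading.

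The size is a matter of timing alone: the first required reading could move from no earlier than about 8 minutes to within 1.5 minutes of the end of inhalation. This rests on the protocol's own windows and on reading section 7.2.2.1 as the complete oximetry schedule; no other section adds an earlier reading. How often the change would matter cannot be derived. It narrows the gap without closing it: the inhalation period and the interval between the 10- and 30-minute readings remain uncovered.

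**What to change.** In sections 7.2.2.1 and 6.2 and in Table 4, require two further spot oximetry readings: one at the end of inhalation, taken with the 90-second cough count, and one at the 5 ± 1 minute breath specimen. Take both at the baseline probe site, in keeping with section 7.2.2.2 ("the same location will be used for each individual subject"). Do not interrupt nebulization for a reading.

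Add a rule for artefact. If a reading meets the section 3.1.3.1 threshold but looks artefactual, repeat it at once and record both values; the repeat value decides whether it counts as a DLT. Leave the 10% threshold and Table 1 as they are. Unscheduled readings count as they do now.

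The cost is one added sentence in each of the three places and two CRF fields, with no new visit or equipment, since staff are already with the subject at both moments. There are two downsides. The DLT count becomes slightly more sensitive: one additional DLT in a cohort of three adds three subjects, and more than one at a dose level stops escalation (Table 1; section 3.2.3). The repeat rule could also set aside a true but very brief fall that was taken for artefact, which is why both values should reach the data safety monitor.

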# 3. INVESTIGATIONAL PLAN

## 3.1 OVERALL DESCRIPTION OF STUDY DESIGN AND PLAN

# 3.1.1 Primary Endpoint

The primary endpoint is the safety of inhaled C-urea in healthy volunteers and in subjects with CF assessed by adverse events, spirometry test results (FEV1 and forced vital capacity [FVC]), and respiratory examinations (respiratory rate, auscultation [presence of wheezing and crackles], pulse oximetry, and related symptoms, such as cough).

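### New wheeze or rales is a stand-alone dose-limiting toxicity, but post-dose auscultation is scheduled only in subjects who already meet the FEV1 criterion

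*Protocol*

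**What the plan says.** Protocol section 3.1.3.1 lists four respiratory events and calls them mandated DLTs. One is an FEV1 fall of 20% of baseline or more. Another, listed separately and without reference to FEV1, is "new wheezes or rales on examination". Section 3.1.1 names auscultation within the primary safety endpoint: "respiratory examinations (respiratory rate, auscultation [presence of wheezing and crackles], pulse oximetry, and related symptoms, such as cough".

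The timing of auscultation is fixed in section 7.2.2.1: "Auscultation, noting the presence of wheezing and crackles, will be performed at baseline and at any assessment at which" FEV1 "decreases at least 20% from baseline". The preceding sentence there has respiratory rate, oximetry and symptoms recorded before every spirometry, at baseline and at 10 and 30 minutes, without any condition.

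The Day 1 list in section 6.2 puts the respiratory examination with auscultation at step 5 and dosing at step 11. After dosing come breath collection, spirometry (step 13: "Perform spirometry after collecting the breath specimen at 10 and 30 minutes after the end of study drug administration") and adverse event assessment (step 14). Table 4 has a single row, "Respiratory examination (respiration rate, auscultation, pulse oximetry, and related symptoms, such as cough", marked once for Day 1 with no post-dose time. Follow-up is by telephone.

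In subjects with CF, two procedures fall between the step 5 examination and dosing: step 7, "Administer albuterol, only to subjects with CF", and step 9, "For subjects with CF only, collect sputum specimen".

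**The concern.** The condition that triggers post-dose listening is the same as the FEV1 DLT. Anyone auscultated on schedule after dosing is already a DLT, and anyone who is not a DLT on FEV1 has no scheduled examination that could reveal wheeze or rales. The separate auscultation criterion does no work unless someone listens outside the plan.

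Cohorts have three subjects, and one DLT decides between escalating and adding three more (Table 1). Review of the maximum dose in healthy volunteers also opens enrolment of the CF and *H. pylori* subjects (section 3.1.3). An undercount would bear on both decisions and leave one component of the primary endpoint largely unobserved after dosing. The protocol regards such events as possible: section 1.3 accepts that inhalation may trigger some bronchospasm, and section 3.2 pretreats CF subjects because mild bronchospasm could occur. Mild bronchospasm could plausibly cause wheeze without a 20% FEV1 fall.

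A secondary point concerns CF subjects. A post-dose finding would be judged *new* against a chest examined before albuterol and before sputum collection, either of which could change chest sounds.

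**Working it through.** **1. Does scheduled auscultation ever change DLT status?** Cross the FEV1 fall with the presence of new wheeze or rales, with no other DLT criterion met:

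| FEV1 fall | New wheeze or rales | Scheduled to be auscultated? | DLT found by schedule | DLT by section 3.1.3.1 |
|---|---|---|---|---|
| below 20% | no | no | no | no |
| below 20% | yes | no | **no** | **yes** |
| 20% or more | no | yes | yes | yes |
| 20% or more | yes | yes | yes | yes |

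Tested at falls of 0, 10, 15, 19.9, 20 and 25%, the schedule finds the same DLTs with and without post-dose auscultation in all 12 combinations. It misses the four with wheeze and a fall below 20%.

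**2. Is it scheduled elsewhere?** No. Section 6.2 and Table 4 give one examination, before dosing. Section 7.2.2.2 says only that findings are noted when auscultation is done. Section 6.3 is a telephone call.

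**3. Effect on escalation (illustration).** The protocol gives no rates. Let *w* be the assumed rate of wheeze or rales without another DLT, and *d* the share of these found off schedule. The detected rate is *p* = *w* with everyone auscultated and *p* = *w·d* as scheduled; *q* = 1 − *p*. Subjects are taken as independent, with no other DLTs and the rule applied mechanically.

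- Table 1 with section 3.2.3 (escalate at 0/3 or 1/6): P = q³ + 3pq²·q³.
- Wording in the synopsis and section 3.1.3 (stop if more than one *additional* subject has a DLT), treating two or three DLTs in the first three as a stop: P = q³ + 3pq²·(q³ + 3pq²).

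Everyone auscultated, Table 1:
- *w* = 0.05: 0.8574 + 0.1354 × 0.8574 = 0.9734
- *w* = 0.10: 0.7290 + 0.2430 × 0.7290 = 0.9061

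Everyone auscultated, other wording:
- *w* = 0.05: 0.8574 + 0.1354 × (0.8574 + 0.1354) = 0.9918
- *w* = 0.10: 0.7290 + 0.2430 × (0.7290 + 0.2430) = 0.9652

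As scheduled, *d* = 0 gives *p* = 0 and P = 1.0000 under both. At *d* = 0.5 the values for *w* = 0.05 and 0.10 are 0.9929 and 0.9734 (Table 1), and 0.9980 and 0.9918 (other wording).

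| Excess chance of escalating | *w* = 0.05 | *w* = 0.10 |
|---|---|---|
| Table 1, *d* = 0 | 0.0266 | 0.0939 |
| Table 1, *d* = 0.5 | 0.0195 | 0.0673 |
| Other wording, *d* = 0 | 0.0082 | 0.0348 |
| Other wording, *d* = 0.5 | 0.0063 | 0.0266 |

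**4. If other DLTs also occur.** Assume a further 5% of subjects have an FEV1 DLT, and use Table 1. The chance of escalating is 0.973 when isolated wheeze or rales goes undetected, whatever its rate. With everyone examined it is 0.906 at an isolated rate of 5% and 0.814 at 10%. The gaps are 0.067 and 0.159, so having no other DLTs is not the least favourable case.

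**5. Cohort expansion under full auscultation.** The chance of exactly one such finding in three subjects is 3w(1 − w)²: 0.1354 at 5% and 0.2430 at 10%.

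**The case against.** The gap is narrower than the schedule alone suggests. FEV1, saturation, respiratory rate and symptoms are recorded in every subject at 10 and 30 minutes, so the measures behind the other three mandated DLTs are covered and a symptomatic subject may well be examined. Wheeze can also surface as an adverse event noted on physical examination (section 8.1), at rescue albuterol (5.1.5), at the symptom-free discharge check (7.2.1.1) or through the 24-hour call (6.3). The data safety monitor sees data daily and can stop escalation at discretion (8.5, 3.2). Section 3.2 does not expect isotonic solutions to cause bronchospasm, so events may be rare. Every probability above rests on an assumed rate, and the 1.00 needs no off-schedule detection at all.

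This limits the size but leaves the defect. None of these routes requires anyone to listen to every subject's chest, and the monitor cannot act on a finding that was never sought.

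On CF subjects, it can be said that *baseline* is ambiguous, since step 8 of section 6.2 gives that name to the post-albuterol spirometry. But step 5 is the only listed step that names auscultation, and section 7.2.1.1 ties baseline to the initial examination. The reading is fair, though secondary.

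Universal auscultation also has a price beyond larger cohorts. If the findings are incidental, Table 1 would stop escalation at a dose level with probability 1 − 0.9734 = 0.03 or 1 − 0.9061 = 0.09. That is a real cost, but it is the protocol's own DLT rule working as written.

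**Conclusion.** The point holds and should be fixed. Followed exactly, the protocol leaves a mandated DLT criterion and named primary-endpoint component unmeasured after dosing in every subject who has not already met the FEV1 DLT. That conclusion needs no assumed rates; it follows from sections 3.1.3.1 and 7.2.2.1.

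The size is unknown. With no other DLTs and isolated rates of 5% or 10%, the chance of escalating past 20 mg is overstated by at most 0.03 or 0.09 under Table 1, and by 0.01 or 0.03 under the other wording. Off-schedule detection reduces this; other DLTs can increase it, as step 4 of the working shows. The criterion can still be met off schedule, but its detection is not systematic.

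**What to change.** Amend section 7.2.2.1, section 6.2 and Table 4 so that every subject is auscultated at the existing 10- and 30-minute assessments regardless of FEV1, alongside respiratory rate and oximetry, with presence or absence of wheeze and crackles recorded on the CRF. In CF subjects, repeat auscultation after albuterol and sputum collection, immediately before dosing, and state that *new* is judged against that examination.

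The cost is a minute or two at time points already scheduled, one extra pre-dose listen in CF subjects, and changes to schedule and CRF wording. The main downside is that an incidental finding can enlarge a cohort: at assumed rates of 5% or 10%, there is a 14% or 24% chance that exactly one of three subjects has one, adding three subjects.
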